## **5.11 Efficacy Analyses**

Statistical tests will be performed using a two-tailed 5% overall significance level, unless otherwise stated. For the primary analysis of the primary endpoint, a multiplicity strategy will be in place to ensure that the familywise error rate (FWER) is controlled at this level across the doses tested (see Section 5.11.7 for details).

All comparisons between treatments will be reported with 95% confidence intervals for the difference.

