#### **5.11.5.1 Change from Baseline to Week 4 in the CGI-S score**

The change from Baseline in the CGI-S score will be analyzed using a similar MMRM as the one for the primary endpoint, replacing baseline CGI-S as covariate in the model. Similar quantities (LS means and their differences, with 95% CIs and p-values) will be presented. Descriptive summaries of observed and change from Baseline values will be presented for all treatment arms.

CGI-S response, defined as a CGI-S score  $\leq 3$ , will also be analyzed separately for each time-point, categorizing any patient with missing data as a non-responder. The number of patients meeting this definition will be summarized descriptively on the mITT analysis set with counts and percentages, including approximate Wald-type 95% CI (with a continuity correction). The difference between treatment arms in the above defined responder rate will be analyzed by reporting the estimated difference in proportions alongside its 95% Wald-type 95% CI with a continuity correction as well as the  $P$ -value derived from Fisher's exact test (using a Monte Carlo approximation to deal with the large sample size). Example SAS code is provided below:

```
ods output RiskDiffCol2 = diff FishersExact = fisher;
proc freq data = ;
  by atptn;
  tables trt01pn*avalc / riskdiff (column = 2 cl = (wald(correct))) chisq;
  exact fisher / mc seed = 123;
run;
```

For the derivation of the exact p-value, it is assumed that the 2x2 table for each visit has the following form:

Treatment	Non-Response	Response
LB-102	a	b
Placebo	c	d

Under the above structure, Fisher's test as implemented in PROC FREQ is defined based on the value  $a$  in the first row/column and the associated one-sided p-values support different alternative hypotheses (the null being that of independence between row and columns):

- Left-sided p-value: supports the alternative that the probability of a patient treated with LB-102 of being a non-responder is smaller than what would be expected under the independence null;
- Right-sided p-value: supports the alternative that the probability of a patient treated with LB-102 of being a non-responder is larger than what would be expected under the independence null.

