Since the hypothesis we're interested in is that patients treated with LB-102 are more likely to be responders than non-responder, a small left-sided p-value supports this hypothesis and as such this is the p-value that will be reported in the table. All CGI-S data will also be listed.

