## 5.11.7 Multiplicity

Results from the analysis of the primary endpoint across the 50 and 75 mg doses will be adjusted for multiplicity using a standard Hochberg procedure. This approach involves ranking the P values from the smallest ( $P_{(1)}$ ) to the largest ( $P_{(2)}$ ) and then comparing  $P_{(2)}$  against 0.05 and if this hypothesis is rejected then reject also the one associated with  $P_{(1)}$ , otherwise  $P_{(1)}$  is further tested

at a local 0.025 two-sided level, and if the test is significant at this level than the null hypothesis associated with it is rejected, whereas the one associated with  $P_{(2)}$  is retained.

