14.2.1.8	Primary Efficacy Endpoint, Change from Baseline to Week 4 in the PANSS Total Score, Site Effect – ITT Analysis Set	Stat IP	
14.2.2	Secondary Efficacy Endpoints		
14.2.2.1.1	Secondary Efficacy Endpoint, Change from Baseline to Week 4 in the CGI-S Score – ITT Analysis Set	Stat IP	14.2.1.1
14.2.2.1.2	Secondary Efficacy Endpoint, Proportion of CGI-S Score Responders – ITT Analysis Set	Stat IP	
14.2.2.2	Secondary Efficacy Endpoint, Change from Baseline to Week 4 in the PANSS Positive Subscale Score – ITT Analysis Set	Stat IP	14.2.1.1
14.2.2.3	Secondary Efficacy Endpoint, Change from Baseline to Week 4 in the PANSS Negative Subscale Score – ITT Analysis Set	Stat IP	14.2.1.1
14.2.2.4	Secondary Efficacy Endpoint, Change from Baseline to Week 4 in the PANSS Marder Factor Scores – ITT Analysis Set	Stat IP	
14.2.2.5.1	Secondary Efficacy Endpoint, Proportion of PANSS Responders at Week 4 (Main Analysis) – ITT Analysis Set	Stat IP	
14.2.2.5.2	Secondary Efficacy Endpoint, Proportion of PANSS Responders at Week 4 (Sensitivity Analysis) – ITT Analysis Set	Stat IP	14.2.2.5.1
14.2.3	Exploratory Endpoints		
14.2.3	Exploratory Efficacy Endpoint, Change from Baseline to Week 4 in CogState Tests Total Scores – ITT Analysis Set	Stat IP	

Table Number	Table Title	Validation Method	Shell Number (if repeat)
14.3	Safety Data		
14.3.1	Displays of Adverse Events		
14.3.1.1	Overall Summary of Treatment-Emergent Adverse Events – Safety Analysis Set	IP	
14.3.1.2	Treatment-Emergent Adverse Events by System Organ Class and Preferred Term – Safety Analysis Set	IP	
14.3.1.3	Treatment-Emergent Adverse Events by System Organ Class and Preferred Term, Poisson Regression – Safety Analysis Set	Stat IP	
14.3.1.4	Treatment Related Treatment-Emergent Adverse Events by System Organ Class and Preferred Term – Safety Analysis Set	IP	14.3.1.2
14.3.1.5	Serious Treatment Emergent Adverse Events by System Organ Class and Preferred Term – Safety Analysis Set	IP	14.3.1.2
14.3.1.6	Treatment Emergent Adverse Events by System Organ Class and Preferred Term and Maximum Severity – Safety Analysis Set	IP	
14.3.1.7	Treatment Emergent Adverse Events by System Organ Class and Preferred Term and Strongest Relationship – Safety Analysis Set	IP	
14.3.1.8	Treatment Emergent Adverse Events Leading to Study Discontinuation by System Organ Class and Preferred Term – Safety Analysis Set	IP	14.3.1.2

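### The CGI-S responder table pairs a one-sided Fisher p-value with a two-sided 95% interval and gives no threshold for reading it

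*SAP*

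**What the plan says.** SAP 5.11 gives the general rule for efficacy tests: "Statistical tests will be performed using a two-tailed 5% overall significance level, unless otherwise stated". It adds: "All comparisons between treatments will be reported with 95% confidence intervals for the difference".

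SAP 5.11.5.1 defines CGI-S response as a score of 3 or lower, analysed at each time-point with missing values counted as non-response. The arms are compared by "reporting the estimated difference in proportions alongside its 95% Wald-type 95% CI with a continuity correction", together with a Fisher exact p-value obtained by Monte Carlo approximation. The section sets out a 2x2 layout, explains what the left-sided and right-sided p-values mean, and concludes that "a small left-sided p-value supports this hypothesis and as such this is the p-value that will be reported in the table". Under that layout the left-sided value supports LB-102 being better than placebo.

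No two-sided Fisher p-value is planned, and no one-sided significance level is given. SAP 5.3 covers only the decimals and formatting of p-values. SAP section 8, which lists changes from the protocol, does not mention the one-sided choice. In SAP section 10 the result goes into Table 14.2.2.1.2, titled "Secondary Efficacy Endpoint, Proportion of CGI-S Score Responders".

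Elsewhere the SAP states sidedness explicitly. The Hochberg second step in SAP 5.11.7 is carried out "at a local 0.025 two-sided level, and if the test is significant at this level", and the sample size in SAP section 3 uses a two-sided 5% level.

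**The concern.** The two statistics in one table row answer different questions. The interval asks whether the arms differ in either direction, with 2.5% in each tail. The p-value asks only whether LB-102 is better, and the only efficacy level the SAP offers for reading it is 5%.

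Two misreadings follow:

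- **In the favourable direction**, an unlabelled p-value below 0.05 can stand beside an interval that includes zero. A reader who applies 0.05 accepts about twice the false-positive chance of the two-sided test.
- **In the unfavourable direction**, a clear placebo advantage is shown as p close to 1, as if there were no signal.

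The continuous CGI-S analysis in the same section reports p-values under the two-tailed default, so two analyses of one scale would carry p-values on different footings. With three doses and four post-baseline visits, up to 3 x 4 = 12 comparisons are affected.

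**Working it through.** **What can be reproduced.** The documents give no figure for CGI-S response: arm sizes are redacted and no response rates are stated. The only design figure is at least 85% power on the primary endpoint (SAP section 3). It serves here only to choose a plausible arm size. With a difference of 8, SD 18, both doses effective, a shared placebo arm and Hochberg, 78 evaluable patients per arm give 85.6% power for at least one dose (200,000 simulated trials). With 25% drop-out that is 78 / 0.75 = 104 randomized per arm. Because missing values count as non-response, the responder denominator is close to the randomized number. Arms of 80, 100 and 120 bracket it.

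**Formulas.**

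- Left-sided Fisher p: P(X <= a), where a is the number of LB-102 non-responders and X is hypergeometric with both margins fixed. With equal arms this distribution is symmetric, so the two-sided p is twice the smaller one-sided p.
- Interval: d ± [1.96 × sqrt(p1(1-p1)/n1 + p0(1-p0)/n0) + (1/n1 + 1/n0)/2].
- Exact p-values are used below. The planned Monte Carlo version differs only by simulation error.

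**Example 1, assumed 44/100 on LB-102 versus 31/100 on placebo.**

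- d = 0.13; standard error = sqrt(0.002464 + 0.002139) = 0.0678; continuity term = 0.01.
- Interval: 0.13 ± (0.1330 + 0.01) = -0.013 to 0.273.
- Left-sided p = 0.0397; two-sided p = 0.0793.
- The row would show p = 0.040 beside an interval that includes zero.

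**Example 2, assumed 25/100 on LB-102 versus 44/100 on placebo.**

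- d = -0.19; standard error = sqrt(0.001875 + 0.002464) = 0.0659.
- Interval: -0.19 ± (0.1291 + 0.01) = -0.329 to -0.051.
- Left-sided p = 0.9986; two-sided p = 0.0072.
- The row would show p near 1 beside an interval that excludes zero in favour of placebo.

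**How often this happens.** For each scenario every possible 2x2 table was enumerated and weighted by its binomial probability. No-effect rates were 20%, 30% and 40%. The true gains were 20 to 30%, 30 to 40%, 30 to 45% and 40 to 50%.

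| Event | Left-sided p | Two-sided p |
|---|---|---|
| p < 0.05 favouring LB-102, no effect, 80-120 per arm | 3.36-3.79% | 1.62-1.94% |
| p < 0.05 favouring LB-102 but interval includes zero, no effect, 80-120 per arm | 1.57-1.91% | 0.00% |
| Same mismatch, true gain of 10-15 points, 80-120 per arm | 9.4-11.8% | 0.00% |
| Same mismatch, no effect, 36 versus 108 (100 mg arm, 1:3) | 1.9-2.2% | 0.4-1.1% |

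The ratio of the two rates in the first row is 1.94 to 2.16.

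**Which threshold matches the interval.** With 90, 108 and 120 per arm and no effect, a left-sided p of 0.025 or less occurs in 1.6-1.9% of trials, and an interval wholly above zero in 1.7-2.0%. A left-sided p of 0.05 or less occurs in 3.5-4.0%. The one-sided value is therefore consistent with the interval when read at 0.025, and not at 0.05.

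**The case against.** The strongest reply is that nothing is hidden. The default in SAP 5.11 allows exceptions, and SAP 5.11.5.1 states one openly, with the table layout and the meaning of each tail. The choice is prespecified. No decision rests on it: the protocol synopsis confines formal testing to the primary endpoint, CGI-S response is not among the secondary endpoints listed in SAP 2.2.2, and a threshold for a descriptive p-value may seem beside the point. The table shells are a separate document and may carry a label. The interval is in the same row, so a careful reader can see a placebo advantage. Even read at 0.05, the one-sided false-positive rate stays below 5%.

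Most of this stands, and it limits the weight of the point. The familywise error rate and the primary conclusion are unaffected. But the exception states only a direction, not a level, and the SAP text does not require a label. SAP 5.11.1 also writes the primary hypotheses directionally, yet SAP 5.11.7 still tests them at two-sided levels, so a directional hypothesis does not by itself explain a one-sided p-value. The result is also tabulated as a secondary efficacy endpoint and will be read as one. A descriptive p-value that can disagree with its own interval describes poorly.

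Two limits on the figures should be kept in view. The near-complete removal of the mismatch holds only for equal arms; for the small 100 mg arm some remains. The count of 12 is inferred from the wording on time-points and arms, because the SAP's 2x2 layout shows one generic LB-102 row.

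**Conclusion.** The concern holds. Followed exactly, the plan can print p below 0.05 beside a 95% interval that includes zero, and p near 1 beside an interval that clearly favours placebo. At 80 to 120 per arm the first mismatch occurs in about 1.6-1.9% of comparisons with no effect and in 9-12% with a true gain of 10 to 15 points. Read at 0.05, the chance of a false positive in favour of LB-102 is about double that of the two-sided Fisher test.

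These frequencies rest on assumed arm sizes, response rates and gains. The inconsistency itself does not depend on them. It is a reporting problem that should be corrected; it does not threaten the trial's main result.

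**What to change.** In SAP 5.11.5.1, replace the choice of the left-sided value with the two-sided Fisher p-value, and show that in Table 14.2.2.1.2. If the sponsor prefers the one-sided value, label it one-sided in the table and state in the SAP that it is read against 0.025.

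The cost is one sentence and one table column; the same 2x2 table is used and no new data or model is needed. There are two downsides. The reported p-value becomes about twice as large when the result favours LB-102. Agreement with the interval is also not perfect, because Fisher and Wald are different methods: at 80 to 120 per arm, a two-sided p of 0.05 or more beside an interval wholly above zero remains in up to 1.8% of trials. For the 100 mg arm (assumed 36 versus 108), the opposite mismatch falls to 0.4-1.1% with no effect but does not vanish.

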#### ***5.11.5.2 Change from Baseline to Week 4 in PANSS positive subscale score***

This endpoint will be analyzed as described in Section 5.11.5.1, both with respect to the modelling strategy (inclusive of the imputation step and with appropriate changes to the baseline measurement to use as a covariate) and the descriptive summary approach.

All PANSS subscale scores will be listed alongside the total score.

#### ***5.11.5.3 Change from Baseline to Week 4 in PANSS negative subscale score***

This endpoint will be analyzed as described in Section 5.11.5.1, both in terms of model to fit and quantities to report.

#### ***5.11.5.4 Change from Baseline to Week 4 in PANSS Marder Factor scores***

This endpoint will be analyzed as described in Section 5.11.5.1, both in terms of model to fit and quantities to report (but with no imputation step), separately for each factor score described in Section 5.2.12.

#### ***5.11.5.5 Response rate, defined as a reduction of $\geq 20\%$ from Baseline in PANSS total score at Week 4***

As described in Table 2, prior to analysis the PANSS score data imputed under a MAR mechanism will be dichotomized as being a responder or non-responder, and then missing data due to discontinuation because of lack of efficacy or drug-related AE as well as any data collected after any relevant ICE (start of emergency or prohibited treatment prior to Week 4) will be imputed as non-responders. The resulting dataset will be analyzed using a logistic regression using the response status at Week 4 as a response and baseline PANSS score, and treatment as covariates, using the below sample SAS code:

```
ods output Diffs = <output-dataset>;
proc logistic data =  descending;
  by _imputation_;
  class trt01p (ref = 'Placebo');
  model response = trt01p baseline / link = logit;
  lsmeans trt01p / diff ilink om oddsratio;
run;
```

From the above, the log odds ratio alongside its standard error will be estimated and then pooled across imputed datasets to return one single estimate, which will be exponentiated (alongside its 95% CI) to obtain an OR for each treatment arm. The proportion of responders at day 28 will also

be descriptively summarized (based purely on observed data), with an approximate 95% CI reported, derived using the following sample SAS code:

```
ods output RiskDiffCol2 = <output-dataset>;
proc freq data = ;
  table trt01p*response / riskdiff (column = 2);
run;
```

This endpoint will also be analyzed by imputing all missing data as non-responders and fitting the same logistic regression as above, from which the OR for each arm will be estimated.

Response status will be listed in the general PANSS listing.

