5.3 Patient Withdrawal/Discontinuation Criteria

All patients are free to withdraw from participation in this study at any time for any reason and without prejudice.

A patient will be considered to have completed the study when they complete the End of Study (EoS) Visit (Visit 7). If a patient is discontinued at any time after randomization into the study, the Investigator will make every effort to follow the patient and complete the follow-up procedures at an Early Termination (ET) Visit as follows:

- Recording of concomitant medications (e.g., prescription and nonprescription medications)
- Full physical examination
- Bodyweight, BMI (derived programmatically from body weight and height measurements), and waist circumference
- Vital signs
- Resting 12-lead ECG (triplicate, further information in Section 8.2.3)
- Collection of blood and urine samples for clinical laboratory tests. Additional information is presented in the footnotes to the schedule of assessments (SoA) (Table)
- Urine pregnancy test for all females of childbearing potential
- Assessment and recording of AEs
- PANSS, PCRS must be administered before PANSS

CGI-S

Confidential Page 43 of 102

- C-SSRS
- AIMS
- BARS
- SAS
- Cogstate test

Patients may be replaced; however, this must be assessed on a case-by-case basis and be approved by the Sponsor or their designee.

The data on ET will be captured in electronic case report form (eCRF) that should be collected for every patient who receives study drug, whether or not the patient completes the study. The reason for any early discontinuation should be indicated on this form. The primary reason for a patient discontinuing early should be selected from the following standard categories:

- Adverse Event: Clinical or laboratory events occurred that, in the medical judgment of the Investigator for the best interest of the patient, are grounds for discontinuation. These events include SAEs and nonserious AEs regardless of relation to the study drug.
- Lack of Efficacy: Worsening of psychotic symptoms.
- Non-compliance with study drug according to the PI.
- *Protocol Deviation*: The patient's findings or conduct failed to meet the protocol entry criteria or failed to adhere to the protocol requirements (e.g., drug non-compliance, failure to return for defined number of visits).

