9.1.6 Assessment of Relationship

Each AE will be assessed as to its relationship to the study drug, based on the following criteria. Although the attribution by the Investigator will be collected for reported events, for analytic purposes a temporal association with the use of the study drug will be assumed sufficient for at least plausible association.

Not related: No causal relationship exists between the study drug and the AE, but

an obvious alternative cause exists, e.g., the patient's underlying

medical condition or concomitant therapy.

Possibly related: A connection with the administration of the study drug appears

unlikely, but cannot be ruled out with certainty. An AE may be considered possibly related if or when it meets 2 of the following

criteria: (1) it follows a reasonable temporal sequence from

administration of the study drug; (2) it could not readily have been produced by the patient's clinical state, environmental or toxic factors, or other modes of therapy administered to the patient; or (3) it follows a known pattern of response to the study drug.

Related: There is a reasonable/plausible possibility that the AE may have been

caused by the study drug.

When assessing the relationship to the study drug, the following criteria will be considered:

Positive rechallenge

• Positive dechallenge (resolution upon stopping the suspect study drug, in absence of other intervention or treatment)

Confidential Page 75 of 102

- Known class effect
- Biological plausibility
- Lack of alternative explanation (e.g., a concomitant drug or disease)

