10.4.4.3 Secondary Efficacy Endpoint(s)

All continuous secondary efficacy variables will be analyzed using similar approaches to what was described for the primary endpoint, using the appropriate Baseline measurement instead of the Baseline PANSS score, without any data imputation.

The secondary efficacy endpoints to analyze in this way are the following:

- Change from Baseline to Week 4 in CGI-S score
- Change from Baseline to Week 4 in PANSS positive subscale score
- Change from Baseline to Week 4 in PANSS negative subscale score
- Change from Baseline to Week 4 in PANSS Marder factor scores

The MMRM model for the above endpoints will allow to estimate the least square (LS) means and their difference between each active dose and placebo alongside their 95% CI and *P* values, which will only be displayed for informative/descriptive purposes (i.e., no multiplicity correction will be implemented).

An additional exploratory endpoint is clinical response, defined as a reduction of ≥20% from Baseline in PANSS total score at Week 4. This will be analyzed consistently with a "composite

Confidential Page 83 of 102

strategy" estimand, where a patient will be considered a responder if the criteria for clinical response are met and none of the ICEs mentioned above has occurred. For the purposes of this endpoint, only study discontinuations related to the treatment (e.g., lack of efficacy, AE related to the underlying condition such as worsening, etc.) will be considered as relevant ICEs and thus contribute to a non-responder status if occurring.

This endpoint will be analyzed using a logistic regression model including treatment and Baseline PANSS score as covariates to estimate the odds ratio of response of any active dose vs placebo.

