
 
• Taking a prohibited medication prior to Week 4
 
• Starting an emergency treatment prior to Week 4
 
 
All of these intercurrent events (ICEs) will be handled via a composite strategy, i.e. patients will be considered as non-responders
	
Missing data at Week 4 because of discontinuation due to ‘Lack of Efficacy’ or a drug-related AE will be imputed as non-responders. For all other missing data, the PANSS total score imputed for the primary analysis of the primary endpoint will be dichotomized as responders or not.
 
As a sensitivity analysis, all missing data will be imputed as non-responders.

Population-level summary measure	Analysis approach
Difference between patients treated with LB-102 (50 or 75 mg QD) and those treated with matching placebo in the PANSS response rate at Week 4 post-baseline.	
This endpoint will be analyzed using a logistic regression model including treatment and Baseline PANSS score as covariates to estimate the odds ratio (OR) of response of LB-102 (50 or 75 mg QD) vs placebo. The model will be fit separately to all imputed datasets and results pooled across imputations to obtain one single treatment effect estimate alongside 95% CI.
 
The same model will also be fit for the sensitivity analysis and a single OR (alongside its 95% CI).

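### PANSS response: SAP 5.11.5.5 as worded lets two small groups be MAR-imputed and counted as responders, although the protocol or SAP Table 2 makes them non-responders

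*SAP*

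**What the plan says.** **Protocol 10.4.4.3** defines response as a reduction of at least 20% in PANSS total score at Week 4, under a composite strategy. Among discontinuations, it counts as non-response "only study discontinuations related to the treatment (e.g., lack of efficacy, AE related to the underlying condition such as worsening, etc".). The rule does not require that the AE be judged drug-related.

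**SAP 2.3, Table 2** gives two rules.
- *Intercurrent events (ICEs).* Prohibited medication or emergency treatment before Week 4 is "handled via a composite strategy, i.e. patients will be considered as non-responders".
- *Missing data.* Missing Week 4 data after discontinuation for lack of efficacy or a drug-related AE is non-response. For all other missing data, "the PANSS total score imputed for the primary analysis of the primary endpoint will be dichotomized as responders or not".

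**SAP 5.11.5.5** puts this into operation. MAR-imputed scores are dichotomized first. Then "missing data due to discontinuation because of lack of efficacy or drug-related AE as well as any data collected after any relevant ICE" is set to non-response.

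**Protocol 5.3** supplies the discontinuation reasons. One is "Lack of Efficacy: Worsening of psychotic symptoms". Another is Adverse Event, of which it says: "These events include SAEs and nonserious AEs regardless of relation to the study drug".

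**Protocol 9.1.6** classes an AE as not related when no causal relationship exists and "an obvious alternative cause exists, e.g., the patient's underlying" medical condition.

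**The concern.** A composite response endpoint should fail patients who left because their psychosis worsened, or who needed another antipsychotic. Read literally, 5.11.5.5 misses some of each.

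1. **Worsening recorded as an AE.** The SAP replaces the protocol's criterion (an AE of the underlying condition) with a different one (a drug-related AE). If a site chooses Adverse Event rather than Lack of Efficacy and judges the event not related, the missing Week 4 score goes to MAR. The same clinical event can then be a certain non-response or a possible response, depending on which box is ticked.
2. **ICE with no Week 4 PANSS.** Table 2 classifies the patient, but 5.11.5.5 recodes only data collected after the ICE. Take a patient who starts a prohibited antipsychotic and is withdrawn because they "failed to adhere to the protocol requirements". They have no Week 4 value to recode, so the imputed status stays.

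At stake are the response rates and odds ratio of one secondary endpoint.

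**Working it through.** **Step 1: follow each patient through the rules.**

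| Patient (no Week 4 PANSS) | Protocol 10.4.4.3 or Table 2 ICE rule | SAP 5.11.5.5 as worded |
|---|---|---|
| Worsening, coded Lack of Efficacy | non-responder | non-responder |
| Worsening, coded AE, possibly related or related | non-responder | non-responder |
| Worsening, coded AE, not related | non-responder (protocol) | MAR-imputed, dichotomized |
| ICE, then leaves for lack of efficacy or drug-related AE | non-responder | non-responder |
| ICE, then leaves for another reason or misses Week 4 | non-responder (Table 2) | MAR-imputed, dichotomized |

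Only rows 3 and 5 are affected. In row 3 the two SAP texts agree with each other and differ from the protocol. In row 5 the ICE and missing-data cells of Table 2 pull in different directions.

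**Step 2: inputs.** The plan gives no response rate to reproduce, and arm sizes are blacked out. From the sample-size section: difference 8, SD 18, drop-out 25%. Assumed: baseline 95, placebo change −10 and hence active −18; mean changes at Weeks 1–4 of −4, −7, −9, −10 (placebo) and −6, −11, −15, −18 (active); SDs 10, 13, 16, 18; visit correlation AR 0.7, AR 0.8 or compound symmetry 0.6.

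**Step 3: chance of an imputed response.** The threshold is 0.20 × 95 = 19 points. SAP 5.11.2 imputes within arm.
- *No post-baseline PANSS:* placebo Φ((−19+10)/18) = 0.309; active Φ((−19+18)/18) = 0.478. The OR is 2.05.
- *Last seen at Week 2, worse by 5* (linear path, multivariate normal; AR 0.7 / AR 0.8 / CS 0.6): placebo 0.137 / 0.078 / 0.071; active 0.225 / 0.136 / 0.130.
- *Last seen at Week 2, improved by 12:* placebo 0.360 / 0.371 / 0.352; active 0.492 / 0.497 / 0.486.

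The composite value is 0 in every case. A separate simulation used the SAP's predictive mean matching and predictor lists (mean Week 4 change −8 to −20, correlation 0.75). It gave 28–53% for a worsening-AE drop-out before Week 1, 13–32% with worsening seen at Week 1, and 34–57% for an ICE patient leaving after Week 2.

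**Step 4: effect on an arm's response rate.** Overstatement = m × P, where m is the share of the arm affected. For m = 5% (20% of drop-outs, as 5/25):
- last seen worse: placebo 5 × 0.071 to 5 × 0.137 = 0.4 to 0.7 points; active 5 × 0.130 to 5 × 0.225 = about 0.7 to 1.1 points;
- no post-baseline PANSS: 5 × 0.309 = 1.5 and 5 × 0.478 = 2.4 points;
- last seen improved by 12: about 1.8 and 2.5 points.

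**Step 5: effect on the OR.** The composite rate is (1−m)r and the SAP rate is (1−m)r + mP, with P for patients last seen worse.

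| m placebo / active | Composite rates | Composite OR | SAP OR |
|---|---|---|---|
| 5% / 5% | 0.293 / 0.454 | 2.00 | 2.02–2.03 |
| 8% / 3% | 0.284 / 0.464 | 2.18 | 2.12–2.15 |
| 3% / 8% | 0.299 / 0.440 | 1.84 | 1.90–1.94 |

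If instead P equals the no-post-baseline values, the SAP OR is 2.05 in all three rows.

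**The case against.** The strongest reply is that both groups are residual and partly a matter of drafting.

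- **Group 1 is narrow.** The protocol defines Lack of Efficacy as worsening of psychotic symptoms, so most such withdrawals should be non-responders already. A reader might infer from 9.1.6 that worsening AEs usually fall outside the SAP rule. The documents do not support that: a link that is unlikely but cannot be ruled out is possibly related, and SAP 5.13.1 counts possibly related and missing relationship as related. This stands; only the unrelated remainder is affected.
- **Section 8 is not silent.** A reader might infer an undeclared change. SAP section 8 does say that treatment discontinuation is no longer an ICE, and it cites Table 2. But the entry is headed as the primary estimand, and the SAP still fails two kinds of discontinuation, so it does not tell the reader that unrelated worsening AEs stop counting.
- **The drug-related wording is the protocol's own primary missing-data rule** (10.4.4.2). Aligning the two is defensible if declared.
- **Section 5.11.5.5 opens by referring to Table 2,** so a programmer may apply the patient-level rule. True, but Table 2's missing-data cell makes no exception for ICE patients, and the reference does nothing for group 1.
- **Early-termination PANSS is requested** (protocol 5.3 and 7.2.14), and SAP 5.2.4 can use it as Week 4 on Days 25–30. This lowers the likely effect and makes the no-post-baseline case an unfavourable scenario.
- **A sensitivity analysis sets all missing data to non-response.** It covers both groups, but it also fails everyone who left for unrelated reasons, so it is not the composite that either document describes.

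**Conclusion.** The rule is wrong as written, with low severity. Followed literally, 5.11.5.5 gives some patients a non-zero chance of response where protocol 10.4.4.3 (group 1) or the Table 2 ICE strategy (group 2) gives zero.

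The effect is small: around half a point to two and a half points on an arm's response rate if 5% of the arm is affected. The odds ratio shifts slightly in either direction, depending on which arm holds more such patients. The shares, baseline, mean changes and correlations are assumptions; the documents supply only the difference, the SD and the drop-out rate.

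A reader might infer that the trial's efficacy conclusion is at risk, or that the error favours LB-102. Neither follows. The primary PANSS analysis and its Hochberg test do not use this rule, response carries no multiplicity-controlled claim, and the direction depends on arm imbalance. A reader might also want emergency treatment defined, or use above the protocol Table 6.2 limits classified drug by drug. The documents give no basis for a particular choice, and this point does not need one.

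**What to change.** Replace the operative sentence in SAP 5.11.5.5, and align the missing-data cell of Table 2, with:

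> After MAR imputation and dichotomization, a patient is a non-responder in every imputed dataset if, before Week 4, they (a) start prohibited medication or emergency treatment, whether or not any later PANSS was collected, or (b) discontinue for lack of efficacy, a drug-related AE, or an AE of worsening schizophrenia or psychosis whatever its relationship to study drug. All other missing Week 4 scores use the dichotomized MAR-imputed value.

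If the sponsor prefers to keep the drug-related limit alone, part (a) is still needed, and SAP section 8 should state explicitly that this departs from protocol 10.4.4.3.

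The cost is one SAP paragraph, one program flag, and agreement before unblinding on which AE terms count as worsening. Discontinuation reason, AE relationship and medication records are already in the eCRF. No new data and no protocol amendment are needed.
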